### 1.2 Secondary Objective

- 1.2.1. To assess the conspicuity of each imaging modality to differentiate radiation necrosis from progressive disease.

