## 2.1 Primary brain tumors

Primary brain tumors are the most common primary brain tumor in the United States, and despite aggressive multimodal therapy with maximum safe resection, radiotherapy in combination with concurrent and adjuvant temozolomide, the median survival of the most aggressive form of primary brain tumor, glioblastoma, in clinical trial populations is **16 months**. There has been an unfortunate stagnation in the ability of non-invasive diagnostics to accurately differentiate between treatment response and failure. Even under optimal circumstances with the use of 'state of the art' diagnostic and therapeutic interventions, less than 15% of patients will survive five years. [8] [9] [10] While the introduction of temozolomide into the first-line standard of care [11] achieved some survival improvement, nearly all patients relapse and treatment options for recurrent disease remain limited and largely ineffective.

The ability to measure the response to treatment is a critical component in evaluating the efficacy of new therapies. Unfortunately, current diagnostic neuroimaging paradigms fail to evaluate treatment response for glioblastoma reliably. The initial landmark imaging evaluation guidelines – the Macdonald criteria – were established in 1990 and was based solely on the assessment of contrast-enhancement as a surrogate for tumor size. Contrast-enhancement is non-specific and reflects the degree of extravasation of a contrast agent across a disrupted blood-brain: changes in contrast-enhancement may be attributable to real progression, imaging technique, treatment (surgery, radiation, or chemotherapy), steroids and parenchymal changes unrelated to the tumor (postsurgical changes, ischemia, seizures). Particularly with the use of multimodal therapy with radiation and temozolomide and new systemic therapies such as bevacizumab, new radiological

phenomena including pseudoprogression and pseudoresponse have added further complexity to assessing treatment response.

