## 7 STATISTICAL CONSIDERATIONS

### 7.1 Definitions

7.1.1 Lesion “**treatment response**” will be defined by size and contrast to noise ratio (CNR). Treatment response will be assessed only in patients with treatment prior to enrollment.

7.1.1.1 Size – treatment response in a single lesion will be considered as a decrease in size of 30%. (see section 5.1)

7.1.1.2 CNR—treatment response will be considered as a decrease in T1 post-contrast CNR of at least 20%. (see section 5.2) by standard T1 post-contrast imaging.

7.1.1.3 Lesions that do not meet these criteria for treatment response will be considered treatment failure.

7.1.2 Disease **recurrence** will be determined by surgical pathology (if available) or at least three months of imaging follow-up. Disease recurrence will be assessed only in patients with treatment prior to enrollment. Imaging findings will be considered recurrent disease in a lesion if:

7.1.2.1 The lesion was initially considered to be a treatment responder.

7.1.2.2 The lesion showed a successive increase in the size of 25% from nadir or a single imaging time point increase of 40%. (see section 5.1)

7.1.2.3 Lesions that do not meet these criteria will be considered radiation necrosis.

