## 7.4 Analysis Plan

Patients with metastasis are expected to have on average 2-3 detectable brain lesions each. Patients with primary brain tumors are expected to have a single lesion. All analyses will be performed on the largest lesion within patients, and some analyses will be repeated on a per-lesion basis.

The CNR for each imaging method will be determined and reported along with the corresponding 95% confidence interval. In secondary analyses, for the conspicuity endpoints, the T1 sequence by MRI will be considered the gold standard, and we will compare the conspicuity of each of the other methods to that of T1 sequencing by using McNemar's test. This analysis will first be performed in the largest lesion per patient, and then analyses will be repeated using all lesions.

If enough follow-up images are obtained (see section 4.5), we will compare the CNR in lesions that respond to treatment to those that do not by using a Wilcoxon rank-sum test. We will compare the CNR between baseline and follow-up within patient by using a Wilcoxon signed-rank test. Also, for those lesions that initially respond, some will subsequently grow in size after the initial response. Of these, some will be considered radiation necrosis and some progressive disease. The CNR will be compared between lesions with necrosis and those that are progressive disease using a Wilcoxon rank-sum test.

Exploratory aims will be analyzed with descriptive statistics. fMRI paradigms will be summarized by the group mean and standard deviation. Patient satisfaction will be reported on a five-point Likert scale and compared between the 7T scan and the most recent clinical scan by using a Wilcoxon rank-sum test.

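### The conspicuity test in section 7.4 compares each method with T1 and never uses necrosis/progression status, so it cannot answer secondary objective 1.2.1

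*Combined protocol and SAP*

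**What the plan says.** The secondary objective (1.2.1) is "To assess the conspicuity of each imaging modality to differentiate radiation necrosis from progressive disease".

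The only test that section 7.4 assigns to conspicuity is a secondary analysis: "for the conspicuity endpoints, the T1 sequence by MRI will be considered the gold standard", and the trial will "compare the conspicuity of each of the other methods to that of T1 sequencing by using McNemar's test". It is run on each patient's largest lesion and then on all lesions, with no restriction to treated patients. The plan does not define conspicuity or the yes/no score that McNemar's test needs. It also does not say whether T1 here means post-contrast T1. Objective 1.1.1 uses T1 as part of quantitative MRI, while sections 5.2 and 7.1.1.2 name post-contrast T1 explicitly.

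A later paragraph of 7.4 does use lesion status: "The CNR will be compared between lesions with necrosis and those that are progressive disease using a Wilcoxon rank-sum test". That paragraph opens with the condition "If enough follow-up images are obtained (see section 4.5") and gives no number. Section 4.5 is the patient survey; follow-up scans are described in 4.6.

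Under 7.1.2, recurrence is assessed only in previously treated patients and "will be determined by surgical pathology (if available) or at least three months of imaging follow-up". Otherwise, "Lesions that do not meet these criteria will be considered radiation necrosis". Section 2.1 says of conventional imaging: "Contrast-enhancement is non-specific and reflects the degree of extravasation of a contrast agent across a disrupted blood-brain", and lists treatment among the causes of a change in enhancement.

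**The concern.** To show that a method separates two conditions, the analysis has to know which condition each lesion has. The McNemar comparison does not. It asks only whether a method and T1 agree on something called conspicuity, and T1 is both the opponent and the named standard.

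The choice of T1 adds to the difficulty. The protocol regards enhancement as non-specific, and treated patients are eligible because a lesion already shows suspicious new or growing signal (3.1). If T1 means post-contrast T1, it may well show necrosis and tumour alike. A method that shows tumour and spares necrosis would then disagree with T1 on exactly the lesions where it is right.

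At stake is the trial's only secondary objective. A significant McNemar result in either direction could be reported as evidence on discrimination when it is not.

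**Working it through.** **1. The plan's own figures.** Section 7.3 gives no power, effect size or discordance rate for conspicuity. Its worked figures are confidence intervals for the mean CEST CNR (mean 14.9, SD 3.0), and they reproduce as mean ± 1.96·SD/√n:
- n = 20: 14.9 ± 1.31, or 13.6 to 16.2
- n = 45: 14.9 ± 0.88, or 14.0 to 15.8

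They do not bear on this point.

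**2. Lesions that can inform 1.2.1.** From 3.3 and 7.3: 100 × 0.90 = 90 tumour patients, of whom half, 45, are treated. The other 55 (45 untreated, 10 non-tumour) enter the McNemar test but cannot have a 7.1.2 status.

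**3. One hypothetical case.** Assume 20 treated lesions, 10 necrosis and 10 progression, all conspicuous on T1. None of these figures is in the documents.
- Perfect discriminator, conspicuous in the 10 progressions only: 10 pairs T1-only, 0 method-only. Exact two-sided McNemar p = 2 × 0.5^10 = 0.00195, against the method.
- Method conspicuous in all 20: no discordant pairs, so it ties with T1.
- Scored against status, AUC = U/(n1·n0), ties counting one half. The perfect method has 100/100 = 1.0. T1 and the all-bright method each have 50/100 = 0.5. The ordering reverses.

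**4. Three readings of the text.** Assume 45 treated lesions, half progressive (22.5 and 22.5), T1 sensitivity/specificity 0.90/0.30, new method 0.85/0.85, and errors independent given status. The p-values are exact, on rounded expected counts.

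| Reading | Favours method | Favours T1 | Result |
|---|---|---|---|
| (i) T1 scored as truth | 0, by construction | 22.5×0.22 + 22.5×0.64 = 19.4 | method agrees in 1 − 19.4/45 = 0.57; T1 in 1.00 |
| (ii) T1 as comparator, positive = called progressive | 22.5×0.085 + 22.5×0.045 = 2.9 positive on method only | 22.5×0.135 + 22.5×0.595 = 16.4 positive on T1 only | p ≈ 0.004; differs, but does not show which is right |
| (iii) Both scored against status | 22.5×0.085 + 22.5×0.595 = 15.3 | 22.5×0.135 + 22.5×0.045 = 4.1 | accuracy 0.85 versus 0.60; p ≈ 0.02 for the method |

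Range over 12 combinations (progression 40–60%; T1 0.90/0.30 or 0.80/0.50; method 0.85/0.85 or perfect), 45 lesions:
- (i) the method scores 0.53 to 0.68 against T1, although its true accuracy is 0.85 to 1.00.
- (ii) T1 always has more positives; p runs from 0.0002 to 0.42.
- (iii) the method is always ahead; p runs from below 0.0001 to 0.14.

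**5. Visibility alone.** Assume 90 lesions, T1 visible in 80% and the method in 95%, independently. Method-only is 90×0.95×0.20 = 17.1 and T1-only is 90×0.80×0.05 = 3.6, p ≈ 0.007 in favour of the method. Here the method beats T1, and still nothing has been learned about necrosis versus progression.

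**The case against.** A reader might infer that section 7.4 always scores a discriminating method as worse than T1. The documents do not support that.

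- McNemar's test treats the two paired methods symmetrically. If T1 is only a comparator, a method can beat it, as step 5 shows. Only scoring T1 as truth rules this out, and 7.4 does not say how scoring works.
- The 10-versus-0 case needs every lesion to be conspicuous on T1. Sections 5.2 to 5.6 draw the lesion region on post-contrast T1, which pushes that way, but 5.1 lets a lesion qualify on T2-weighted imaging. If 10 other lesions were seen by the method and not by T1, discordance would be 10 versus 10 and p = 1.
- The argument from non-specific enhancement applies only if T1 means post-contrast T1, which 7.4 does not state.
- The plan does have an analysis by status. The rank-sum statistic divided by n1·n0 is the AUC, so discrimination is addressed for each method separately, and a status-based replacement would depend on the same follow-up.

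All four stand as limits on how far the point reaches. None makes the McNemar test a measure of discrimination. The rank-sum test carries an unquantified follow-up condition, is not linked to 1.2.1 or to conspicuity, and makes no comparison with T1.

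**Conclusion.** The point holds in a limited form. The test named for the conspicuity endpoints cannot show whether any method separates necrosis from progression, because status does not enter it and more than half of the expected patients (55 of 100) cannot have the status in question. This follows from the text and needs no assumed accuracy.

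The direction of any error is not fixed. It is certain to go against the method only if T1 is scored as truth. If T1 is a comparator, correct discrimination can be counted as a deficit, and p = 0.002 is one hypothetical illustration of that, not an expected result. The other figures rest on assumed prevalence, accuracies and conditional independence, since the documents give none.

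What the plan lacks is a status-based comparison of each method with T1, and a statement that the McNemar result concerns visibility only.

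**What to change.** Change section 7.4 as follows.

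1. Call T1 the comparator, drop the term gold standard, and state whether it is T1 post-contrast.
2. State the yes/no conspicuity rule used in McNemar's test, and describe its result as visibility only, not as evidence on 1.2.1.
3. For 1.2.1, take the 7.1.2 status (pathology where available, otherwise follow-up) as the reference in treated lesions. Report each method's AUC for progression versus necrosis with a 95% CI, and the paired AUC difference from T1 post-contrast. State the lesion set: the rank-sum sentence in 7.4 follows on from lesions that first responded and then grew, which is narrower than all treated lesions.
4. Add a sensitivity analysis in pathology-labelled lesions only. Without pathology, recurrence requires initial response, which draws on T1 post-contrast CNR (7.1.1.2) and on size that may be measured on T1 post-contrast (5.1.2).
5. Correct the cross-reference for follow-up images from 4.5 to 4.6.

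The cost is analysis wording; the CNR values and labels are already planned. The downsides are fewer lesions, wider intervals, and a follow-up label that is not fully independent of T1, so the paired comparison with T1 needs that caveat wherever it is reported.

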## 3.3 NUMBER OF PARTICIPANTS

One hundred (100) patients will be studied. Up to twenty (20) healthy volunteers will be studied for the purposes of MRI sequence optimization.

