## 7.3 Sample Size

The healthy volunteers' data will only be used for fMRI sequence optimization, quality assurance and will not yield data for the study. The optimization scans on healthy volunteers will not affect the statistical results.

Patients will be divided into 5 groups as discussed above. It is assumed that 90% of patients enrolled will represent either brain metastasis or primary brain tumor, approximately half in each category. We also expect approximately half of each group to have received treatment. We thus expect to have approximately 20-25 patients in each of the first four groups (metastasis with and without treatment and primary brain tumor with and without treatment). The other 10% will be in group 5 and are assumed to be non-tumor mimics of malignancy (for example, stroke, demyelinating disease).

For the primary endpoints, the objective is to calculate the contrast-to-noise ratio (CNR) or equivalent parameter for each method for both primary brain tumors and metastases separately by whether the patient has received treatment. For each imaging modality, we will calculate the CNR separately in the largest lesion/metastasis per patient as well as in all study lesions (see 5.1.3). As an example, for CEST, under the assumption of only a single lesion per patient and an expected mean CEST CNR of 14.9 and corresponding standard deviation of 3.0, 20 patients in a group will give a 95% confidence interval between 13.6 and 16.2. [40] Similar calculations apply for the CNR for each of the other imaging modalities.

We may also combine groups for the purpose of analysis. Continuing the above example, with 45 patients in a group, and the same assumed mean and standard deviation, a 95% confidence interval around the CEST CNR will range from 14.0 to 15.8. Again, similar calculations apply for other imaging modalities.

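### Section 7.4 relates CNR to treatment response only through a yes/no label and never uses the amount of lesion change; if the relation is graded, that costs roughly 7 to 34 points of power under stated assumptions.

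*Combined protocol and SAP*

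**What the plan says.** Section 7.1.1 defines response in a lesion by two measurements. For size: "treatment response in a single lesion will be considered as a decrease in size of 30" (per cent). For contrast: "treatment response will be considered as a decrease in T1 post-contrast CNR of at least 20" (per cent). Everything else takes the opposite label: "Lesions that do not meet these criteria for treatment response will be considered treatment failure". Response is assessed only in patients treated before enrolment.

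Section 7.4 then states, on condition that enough follow-up images are obtained: "we will compare the CNR in lesions that respond to treatment to those that do not by using a Wilcoxon rank-sum test". All analyses use the largest lesion per patient, and some are repeated per lesion.

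The expected numbers come from sections 3.3 and 7.3: "One hundred (100) patients will be studied", "It is assumed that 90% of patients enrolled will represent either brain metastasis or primary brain tumor", and "We also expect approximately half of each group to have received treatment". Section 7.3 also gives "approximately 20-25 patients in each of the first four groups". For the responder comparison the document states no power, significance level, effect size, responder share or follow-up rate.

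**The concern.** Both inputs to the label are continuous. Section 5.1.2 measures the longest diameter, and section 5.2 records the signal intensities behind the T1 post-contrast CNR. The percentage change has to be calculated before either cut can be applied, and is then dropped. On the size criterion, a lesion that shrinks by 29% is pooled with one that doubles and separated from one that shrinks by 31%. The plan gives no source for the two cuts; the response guidelines discussed in section 2.1 are background and are not named as their origin.

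Nothing else in section 7.4 recovers the lost information. The signed-rank test compares CNR between baseline and follow-up within patients. The necrosis-versus-progression test uses another two-class label. At stake are the chance of seeing a real graded association in a small group of treated patients, and any estimate of its strength.

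**Working it through.** **The plan's own figure.** Section 7.3 gives a 95% interval for a CEST CNR with mean 14.9 and SD 3.0. The formula is mean ± 1.96 × SD/√n.
- n = 20: 14.9 ± 1.96 × 3.0/√20 = 13.59 to 16.21 (stated 13.6 to 16.2).
- n = 45: 14.9 ± 1.96 × 3.0/√45 = 14.02 to 15.78 (stated 14.0 to 15.8).

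Both reproduce. They concern the primary estimation objective and say nothing about the responder comparison.

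**Number of treated patients.** 100 × 0.90 × 0.5 = 45 expected, or about 22 per tumour type. From 20-25 per group, the two treated groups together give 2 × 20 = 40 to 2 × 25 = 50. Missing follow-up lowers this.

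**Assumptions the document does not supply.** Two-sided 5% level; correlation of 0.3 to 0.5 between 7T CNR and percentage change; 20% to 50% responders; 22 to 45 evaluable patients; bivariate normal data, which means a graded relation.

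**Simulation under a graded relation.** Responders are the lesions with the greatest decrease. A Spearman test on the change is compared with a continuity-corrected rank-sum test of CNR between the two classes. Power at n = 45, in per cent:

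| Correlation | Responders | Spearman | Rank-sum | Loss (points) |
|---|---|---|---|---|
| 0.3 | 50% | 47.7 | 32.7 | 15 |
| 0.3 | 30% | 48.3 | 30.9 | 17 |
| 0.3 | 20% | 47.5 | 25.7 | 22 |
| 0.4 | 50% | 73.5 | 54.4 | 19 |
| 0.4 | 30% | 73.6 | 50.4 | 23 |
| 0.4 | 20% | 74.3 | 43.3 | 31 |
| 0.5 | 50% | 92.4 | 77.2 | 15 |
| 0.5 | 30% | 92.6 | 73.7 | 19 |
| 0.5 | 20% | 92.2 | 64.9 | 27 |

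With fewer evaluable patients, at correlation 0.4 and 30% responders, power is about 55% against 36% at n = 30, and 41% against 25% at n = 22. Over the whole grid (n = 22 to 45) repeated runs put the loss at roughly 7 to 34 points. With no association, both tests reject in about 5% of runs or slightly fewer.

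**Analytic cross-check.** Cutting a normal variable at responder share p multiplies the correlation by φ(z_p)/√(p(1−p)), which is 0.759 at p = 0.3. Approximate power is Φ(atanh(r) × √(n−3) − 1.96). For n = 45 and r = 0.4:
- Full scale: atanh(0.4) × √42 − 1.96 = 0.785, so power is 78%.
- After the cut: r = 0.4 × 0.759 = 0.304, so atanh(0.304) × √42 − 1.96 = 0.07 and power is 53%.

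The loss is about 26 points, close to the simulated 23.

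**Outside the grid (n = 45).** The loss falls to about 6 to 7 points at correlation 0.2 or 0.6 with an even split. It rises to about 29 to 47 points with 10% responders and correlation 0.3 to 0.5.

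**Simulation under a step.** If CNR differs by 0.9 SD between the classes exactly at the cut, and is unrelated to the amount of change within a class, the order reverses. At n = 45 with 20% to 50% responders, the rank-sum test leads by about 12 to 27 points.

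**The case against.** The strongest reply is that the loss comes from the assumed shape. The document speaks of lesions in distinct states: responder or failure, necrosis or progressive disease. If CNR differs between states and not along the amount of shrinkage, the planned test is the better one. In one simulation where the cut separated the states only imperfectly (n = 45, 30% responders), it still led by 65% to 55%. This stands. The power figures are conditional on a graded relation, and a reader who infers that the plan simply forfeits a fixed amount of power goes further than the document allows. Equally, the document gives no reason to expect a step exactly at these two cuts.

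The importance is also limited. The comparison serves no listed objective: the primary is CNR estimation, the secondary is necrosis versus progression, and the exploratory aims lie elsewhere. It is conditional on follow-up. A reader might infer that the trial's main conclusions are underpowered, but nothing in section 7.3 or 7.4 rests a power claim on this test. Nor is 45 a ceiling: it is an expected number, and the stated group sizes allow 50.

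There are practical objections too. Follow-up is standard-of-care imaging (section 4.6), so a percentage change needs a rule for which scan counts. Size may be read on T2 FLAIR or T1 post-contrast images (section 5.1.2), so the sequence must match. Response rests on two measures, and the text does not say how they combine; the simulation cuts only one, so it approximates the loss. Two outcomes for four methods give eight correlations. These points shape the remedy without removing its value.

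Finally, whether CNR differs between responders and failures is a legitimate question in its own right. That argues for adding an analysis, not for replacing or demoting the planned one.

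**Conclusion.** The point holds as a matter of lost information. The plan relates CNR to treatment response only through a yes/no label, although the continuous changes must already be in hand, and it offers no estimate of the strength of the relation. The missing estimate does not depend on any simulation. The power cost of about 7 to 34 points does: it holds for a graded relation within the assumed grid, and it reverses if CNR changes only as a step at the cut.

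This is a worthwhile, inexpensive improvement to a conditional, non-primary analysis. It is not an error in a stated figure and does not touch the primary objective. The document does not support the stronger conclusion that the responder comparison is invalid.

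**What to change.** In section 7.4, add the following for each of the four study methods (quantitative MRI, CEST, Adv Diff, Adv ASL), using the largest lesion per patient:
- the Spearman correlation, with 95% confidence interval, between lesion CNR or its equivalent parameter and the percentage change in longest diameter;
- the same with the percentage change in T1 post-contrast CNR as the outcome.

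State in advance which single follow-up scan supplies the change, and require the same sequence at both times. Ranks cope with lesions that disappear and with skewed growth. Keep the planned responder/failure rank-sum comparison alongside. Report the correlations as estimates, without a multiplicity-adjusted claim.

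The cost is a few sentences in section 7.4, a scan-selection rule, and 4 × 2 = 8 further estimates to report. No new scans, readers or patients are needed.

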## 3 ELIGIBILITY

### 3.1 Inclusion Criteria

#### Patients

- 13 years old and above.
- Written Informed consent must be obtained by the patient (age 13-17)'s parent or legally authorized representative (LAR)
- Patients must meet one set of inclusion criteria:
  - Newly identified and untreated primary brain tumor or metastasis of at least 5 mm or greater in size.
    - Suspected central nervous system neoplasms will require agreement from a study neuroradiologist and a study neurosurgeon, neuro-oncologist, or a radiation oncology that a lesion exists that is most likely either a primary brain tumor or a metastasis.
    - Patients with suspected brain metastasis must also have a history of solid organ malignancy.
  - History of primary brain tumor or metastasis treated with surgery, radiation, chemotherapy, or immunotherapy with new or increasing signal on MR imaging that is suspicious for progressive disease (treatment failure).
    - Suspected recurrent neoplasms will require agreement from a study neuroradiologist and a study neurosurgeon, radiation oncologist, or neuro-oncologist that lesion behavior is suspicious for recurrent disease.

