## 4.6 Imaging Time Points

4.6.1 A single research imaging session will be planned for each patient. However, patients will still undergo follow-up imaging scans as part of their standard of care. These follow-up scans will serve as the basis for statistical analyses that consider treatment response or disease recurrence.

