## 4.7 Conclusion of Study Participation:

4.7.1 Completion of planned study or volunteer scan.

4.7.2 Upon patient or volunteer request.

4.7.3 Death.

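### As most directly read, the necrosis/progression label compared in 7.4 describes a regrowth after the only 7T scan, not the suspicious signal that was scanned; 3.1, 4.6.1, 7.1.2 and 7.4 must be reconciled

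*Combined protocol and SAP*

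**What the plan says.** All references are to the combined protocol and SAP.

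- **Objective (1.2.1).** "To assess the conspicuity of each imaging modality to differentiate radiation necrosis from progressive disease".
- **Entry of treated patients (3.1).** They need "new or increasing signal on MR imaging that is suspicious for progressive disease (treatment failure".
- **Imaging (4.6.1, 4.7.1).** "A single research imaging session will be planned for each patient". Patients continue with clinical follow-up imaging, and "These follow-up scans will serve as the basis for statistical analyses that consider treatment response or disease recurrence". Participation ends at "Completion of planned study or volunteer scan".
- **Response (7.1.1).** Assessed only in patients treated before enrolment: a 30% fall in size, and a fall of at least 20% in T1 post-contrast CNR. Anything else is treatment failure (7.1.1.3).
- **Recurrence (7.1.2).** Decided by "surgical pathology (if available) or at least three months of imaging follow-up". On imaging there are two conditions. The first is "The lesion was initially considered to be a treatment responder" (7.1.2.1). The second is growth: a successive 25% rise from nadir, or 40% at one time point (7.1.2.2). Lesions that fail these conditions are called radiation necrosis (7.1.2.3).
- **Analysis (7.4).** The response comparisons depend on having sufficient follow-up imaging. The text then says that "for those lesions that initially respond, some will subsequently grow in size after the initial response", divides those regrowths into necrosis and progression, and compares CNR between the two with a Wilcoxon rank-sum test. It does not say which scan supplies the CNR.

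**The concern.** A test of whether an imaging method differentiates two conditions needs the measurement and the label to refer to the same lesion state. Here the measurement is made once, on a signal that is suspicious on that day. The label, as 4.6.1 and 7.4 most directly read, is earned later: the lesion must respond on follow-up, then regrow, and the regrowth is what is classified. The rank-sum test would then ask whether CNR at 7T predicts the nature of a future regrowth, which is not what objective 1.2.1 asks. A method that separated necrosis from progression well on the day of the scan could show no difference.

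The lesions most informative for the objective are also the ones most at risk. Those truly progressing at 7T would be left out of the test or counted as necrosis.

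**Working it through.** **The plan's own figures.** The only sizing in 7.3 is a 95% confidence interval for mean CEST CNR, using mean 14.9 and SD 3.0. The formula is mean ± 1.96 × SD/√n.

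- n = 20: 14.9 ± 1.96 × 3.0/√20 = 14.9 ± 1.315, giving 13.585 to 16.215 (stated: 13.6 to 16.2).
- n = 45: 14.9 ± 1.96 × 3.0/√45 = 14.9 ± 0.877, giving 14.023 to 15.777 (stated: 14.0 to 15.8).

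Both reproduce. Neither bears on the necrosis/progression test, for which 7.3 gives no number, effect size or power. The population it draws on follows from 7.3: 100 patients × 0.90 with tumour × 0.5 treated = 45.

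**Order of events.** The rest is a reading of the text.

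1. Section 4.6.1 plans one 7T session and makes later clinical scans the basis for both response and recurrence. Section 4.7.1 closes participation at the scan. No repeat 7T scan is planned.
2. Section 7.4 makes the responder comparison conditional on follow-up imaging. Had response been established before enrolment, that condition would be unnecessary. (7.4 cites section 4.5 for the follow-up images. That section is the patient survey; follow-up imaging is in 4.6.)
3. The order is therefore 7T scan, response, regrowth, label. An imaging label of progression needs at least 1 follow-up scan to show response plus 1 to show a 40% rise, so 2 scans after 7T. It needs 1 + 2 = 3 if a successive rise means two increases.

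**Treated lesions traced through the rules on this reading**

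| Course after the 7T scan | 7.1.1 | Imaging label under 7.1.2 | Enters the 7.4 test? |
|---|---|---|---|
| Progressing and keeps growing | Failure | Fails 7.1.2.1, so necrosis by default | No, not an initial responder |
| Responds, then regrows | Response | Progression or necrosis, for the later regrowth | Yes |
| Responds, never regrows | Response | Necrosis by default | No |
| Surgical pathology soon after 7T | Not needed for the pathology route | Settled by pathology, close to the 7T date | Not stated |

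The first row is the central difficulty. The first and third rows also show that 7.1.2.3 assigns necrosis to lesions that 7.4 does not consider at all.

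**The other reading.** Suppose the response and nadir came from scans before enrolment. An increasing signal then fits 3.1 well, and later follow-up acts as a delayed reference standard. But 3.1 also admits new signal. A genuinely new signal has no earlier size from which a response or nadir could be taken, so it cannot satisfy 7.1.2.1. This reading also sits badly with 4.6.1.

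**Which CNR.** Quantitative MRI, CEST, Adv Diff and Adv ASL are planned only in the 7T session (4.4, 4.6.1), so for these the CNR or equivalent parameter can only be the 7T value. A T1 post-contrast CNR could come from a later clinical scan (7.1.1.2).

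**The case against.** The best defence is that the timing is not fixed. Treated patients enter with a signal already new or increasing, response is assessed only for treatment given before enrolment, and no section says the response or nadir must post-date the 7T scan. A coherent sequence is treatment, response, growth, enrolment, 7T, then pathology or three or more months of imaging as an ordinary delayed reference standard. This stands as a possible reading, and it is why the point is one of reconciliation. It does not dispose of the concern, because 4.6.1 and 7.4 point the other way and new signal fits neither route.

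It is also fair that 7.4 says only CNR, and that its comparison of baseline with follow-up within patient must draw on clinical scans. A T1 post-contrast CNR at regrowth is therefore possible. That does not help the four methods that objective 1.2.1 needs and that are acquired only at 7T.

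Stronger inferences that the documents do not support:

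- **That the signal leading to enrolment is not classified at all.** Pathology can label it, and 7.1.1.3 and 7.1.2.3 place every remaining lesion in a default class. The difficulty is that the default can be wrong, not that it is absent.
- **That the 7T scan precedes the labelled event by a known number of months.** No follow-up scan interval is given, so only scan counts can be derived, and only on the post-7T reading.
- **That all 45 expected treated patients are affected in the test.** This is the population it draws on; 7.4 restricts the test to responders that regrow.

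**Conclusion.** The concern holds as an unresolved conflict with a probable adverse reading. Taken most directly, the plan compares CNR from the 7T-only methods across labels that belong to a later regrowth. A lesion progressing at 7T that simply keeps growing is called necrosis by default or left out. A reader might infer that the documents fix the regrowth after the 7T scan; they do not, because 3.1 and 7.1 leave room for a response before enrolment.

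The effect is confined to the imaging-labelled part of one secondary analysis, which is conditional and unsized. It is nevertheless the only analysis in 7.4 that uses the distinction in objective 1.2.1, since the McNemar comparison with T1 does not. CNR estimation by malignancy type and treatment status is unaffected. The conclusion rests on reading follow-up scans in 4.6.1 as scans after the 7T session, and on the absence of any named baseline, nadir or index scan.

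**What to change.** Amend 7.1.2 and 7.4, and bring 4.6.1 into line with 3.1, before any labels are assigned:

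1. Define the index event as the signal present on the 7T date, and state that the 7T CNR is the one compared.
2. Label that same signal by pathology obtained after the 7T scan, or by at least three months of imaging follow-up.
3. Take prior response and nadir from pre-enrolment clinical scans where they exist, and name the scans used.
4. For new signal with no earlier response or nadir, drop the requirement of an initial response, and measure later change against its size on the 7T date.
5. List lesions that respond and regrow only after 7T separately, outside the rank-sum test.
6. Make 7.1.2.3 and 7.4 agree on which lesions can be called necrosis, and correct the cross-reference from 4.5 to 4.6.

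The cost is wording plus review of prior clinical scans; no extra patients or 7T sessions are needed. The downside is that fewer lesions may remain in the test, because later regrowths move to a listing. The number entering should be reported.
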